## 7. TREATMENT COMPLIANCE

Study drugs (JNJ-63723283 and daratumumab) will be administered by qualified site staff, and the details of each administration will be recorded in the case report form (CRF). Additional details are provided in the SIPPM. A patient diary card may be used to record drugs taken at home to prevent IRR (eg, pre-infusion medication).

## 8. PRESTUDY AND CONCOMITANT THERAPY

All prior treatments for malignancies, including those since diagnosis, must be recorded at Screening. Throughout the study, investigators may prescribe any concomitant medications or treatments deemed necessary to provide adequate supportive care except for those listed in Section 8.3. The Sponsor must be notified in advance (or as soon as possible thereafter) of any instances in which prohibited therapies are administered.

Routine systemic use of the following concomitant medications will be collected in the CRF and recorded in the source documents beginning with signing of the ICF to PD or until the start of subsequent anticancer treatment, if earlier: growth factors, transfusions, anti-infectives (antibacterials, antivirals, and antimycotics), corticosteroids, anti-arrhythmics and other cardiac supportive therapy, anti-epileptics, centrally acting psychiatric medication, anti-histamines and other medications targeting postinfusion systemic reactions, bisphosphonates, and any anticancer therapy (including radiation).

The use of concomitant medications used to treat adverse events or any infusion-related reactions will be collected in the CRF and recorded in the source documents beginning with the signing of the ICF until PD.

Prestudy therapies administered up to 30 days before first dose of study drug must be recorded at Screening. Concomitant therapies described above must be recorded throughout the study beginning with start of the first dose of study drug until the end of treatment assessment. Concomitant therapies should be recorded beyond 30 days after the last dose of study drug only in conjunction with serious adverse events that meet the criteria outlined in Section 12.3.2, Serious Adverse Events.

## 8.1. Recommended Therapies

## 8.1.1. Bisphosphonate Therapy

Bisphosphonate therapy is strongly recommended for all subjects with evidence of lytic destruction of bone or with osteopenia. Bisphosphonate therapy is recommended to be continued per treatment guidelines (Moreau 2017; NCCN 2017). Commercially available IV bisphosphonates (pamidronate and zoledronic acid) are preferred when available, and should be used according to the manufacturer's recommendations, as described in the prescribing information, for subjects with osteolytic or osteopenic myelomatous bone disease. Oral

bisphosphonates may be used as alternatives if IV bisphosphonates are not available at the study site. Investigators should use the same route of bisphosphonate therapy for all subjects at their sites. Subjects with evidence of lytic destruction of bone or with osteopenia who are not using a bisphosphonate prior to first study drug administration should start a bisphosphonate as soon as possible during Cycle 1 or 2 of treatment. Investigators should not start bisphosphonate therapy during the study, unless it has been agreed with the Sponsor that there is no sign of disease progression.

## 8.1.2. Therapy for Tumor Lysis Syndrome

Subjects should be monitored for symptoms of tumor lysis syndrome. Management of tumor lysis syndrome, including hydration for abnormal laboratory test results such as hyperkalemia, hyperuricemia, and hypocalcemia, is highly recommended. High-risk subjects (ie, those with a high tumor burden) should be treated prophylactically in accordance with local standards (eg, rehydration, diuretics, allopurinol 300 mg daily, and medication to increase urate excretion). Subjects are to be provided prophylactic therapy to manage IRRs as described in Section 6.1.2 for daratumumab.

## 8.1.3. Therapy for *Pneumocystis carinii/jirovecii*

Pneumocystis carinii/jirovecii pneumonia (PCP) prophylaxis should be considered, as per institutional guidelines.

## 8.1.4. **Prophylaxis for Herpes Zoster Reactivation**

Antiviral prophylaxis should be considered for the prevention of herpes zoster virus reactivation.

## 8.2. Permitted Therapies

Subjects are to receive full supportive care during the study. The following medications and supportive therapies are examples of support therapies that may be used during the study:

- Antivirals
- Granulocyte colony stimulating factors, erythropoietin, and transfusion of platelets and red cells is allowed, except as prophylaxis during Cycle 1
- Prevention of constipation (eg, adequate hydration, high-fiber diet, and stool softeners if needed)
- Prophylactic antiemetics, with the exception of corticosteroids
- Loperamide is recommended for the treatment of diarrhea, starting at the time of the first watery stool. The loperamide dose and regimen is according to institutional guidelines. Prophylactic loperamide is not recommended.
- Adequate hydration is recommended for prevention of myeloma-related kidney disease.

- Oral contraceptives
- Hormone-replacement therapy

Other symptoms may be managed according to institutional guidelines provided prohibited therapies are not administered (see Section 8.3).

In general, investigators should manage subject care with supportive therapies as clinically indicated per local standards.

## 8.3. **Prohibited Therapies**

Use of the treatments listed below is prohibited during the study:

- Other agents that target CD38, PD-1 or its ligand, PD-L1.
- Concomitant administration of any other antineoplastic therapy for the intention of treating multiple myeloma is prohibited, including medications used for other indications that have anti-myeloma properties (eg, interferon and clarithromycin). Continuation of study treatment (during or after emergency orthopedic surgery or radiotherapy because subject benefit) may only occur in the absence of disease progression and after consultation with and approval by the Sponsor.
- Emergency radiotherapy may consist of localized radiotherapy for pain control or for stabilization of an extensive bone lesion at high risk of pathologic fracture or damage to surrounding tissues in a subject in whom delay of systemic therapy is not appropriate. Such local radiotherapy is to occur within the first 2 cycles of treatment and the absence of evidence of disease progression is to be reviewed and approved by the Sponsor.
- Concomitant administration of approved or investigational agents with activity against or under investigation for multiple myeloma is prohibited (including but not limited to conventional chemotherapies, IMiDs, or proteasome inhibitors). Systemic corticosteroids (>10 mg prednisone per day or equivalent for over 5 days) other than those given for IRRs, as described in Section 6.2.2 should be avoided. Nonsteroidal anti-inflammatory agents should be avoided to prevent myeloma-related kidney disease.
- Typically, IV contrast is not used in CT scanning of subjects with secretory multiple myeloma because of the risk to the kidney. If administration of IV contrast is necessary, then adequate precautions including hydration are indicated.
- Any live, attenuated vaccine within 4 weeks prior to administration of study drug or during treatment or within 5 months following the last JNJ-63723283 dose.

The Sponsor must be notified in advance (or as soon as possible thereafter) of any instances in which prohibited therapies are administered.

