## 4.2. Exclusion Criteria

Any potential subject who meets any of the following criteria will be excluded from participating in the study:

- 1. Received any of the following prescribed medications or therapies in the past:
  - Anti-CD38 antibody, including daratumumab
  - Anti-PD-1 and anti-PD-L1 antibodies
- 2. Received any of the following prescribed medications or therapies within the specified period:
  - Antimyeloma treatment within 2 weeks or 5 pharmacokinetic half-lives of the treatment, whichever is longer, prior to first administration of study drug. The only exception is emergency use of a short course of corticosteroids (equivalent of dexamethasone 40 mg/day for a maximum of 4 days) for palliative treatment prior to first administration of study drug.
  - An allogenic stem cell transplant (SCT) at any time; or autologous SCT within 12 weeks prior to first administration of study drug.
  - Other investigational agent (including investigational vaccines), participation in another clinical study with therapeutic intent, or used an invasive investigational medical device within 28 days or 5 pharmacokinetic half-lives of the investigational agent (whichever is longer) prior to first administration of study drug.
  - Systemic radiotherapy within 14 days prior to first administration of study drug.
- 3. Plans to undergo a stem cell transplant prior to progression of disease on this study (these subjects should not be enrolled to reduce disease burden prior to transplant).
- 4. History of malignancy (other than multiple myeloma) within 2 years prior to first administration of study drug (exceptions are squamous and basal cell carcinomas of the skin and carcinoma in situ of the cervix, or malignancy that in the opinion of the investigator, with concurrence with the Sponsor's medical monitor, is considered cured with minimal risk of recurrence within 3 years).
- 5. Clinical signs of meningeal involvement of multiple myeloma.
- 6. Either of the following:

- Clinical Protocol 54767414MMY2036 Amendment 2
- Known chronic obstructive pulmonary disease (COPD) with a forced expiratory volume in 1 second (FEV1) <50% of predicted normal. Note that FEV1 testing is required for subjects suspected of having COPD and subjects must be excluded if FEV1 is <50% of predicted normal.

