## 6.2.2. Dose Delay

Dose delay is the primary method for managing JNJ-63723283-related toxicities. In the event of a toxicity that meets the criteria below or is otherwise considered to be clinically significant by the treating physician, treatment will be held and supportive therapy administered as clinically indicated. If clinically significant drug-related toxicity is present, treatment should be delayed until the toxicity resolves (with or without supportive therapy) to baseline or Grade  $\leq 1$  except for alopecia, hyperthyroidism and rash for which resolution to  $\leq$ Grade 2 is required for subsequent treatment. If the toxicity does not resolve to  $\leq$ Grade 1 or baseline within 12 weeks of identification of the toxicity, withdrawal from the study is recommended unless otherwise agreed to by the Sponsor medical monitor and the investigator based on evidence of clinical benefit.

Dose delays will be required if:

- Grade 2 pneumonitis (recurrent Grade 2 pneumonitis, study drug must be permanently discontinued)
- Grade 2 or 3 diarrhea or colitis
- Grade 2 nephritis with creatinine >1.5 to 3.0 x upper limit of normal (ULN)
- Grade 2 or 3 creatinine elevation
- Grade 2 elevation in aspartate aminotransferase (AST) or alanine aminotransferase (ALT) (3-5 x ULN) except for subjects with tumor involvement in the liver at baseline, or total bilirubin (1.5-3 x ULN) except in subjects with congenital bilirubinemia, such as Gilbert syndrome (direct bilirubin 3 x ULN)
- Symptomatic endocrinopathies (including hypothyroidism, hyperthyroidism, hypophysitis, adrenal insufficiency, and diabetes)

- Grade 3 rash
- Grade  $\geq$ 3 non-irAEs (except for hematologic toxicities not attributed to JNJ-63723283)

The criteria for discontinuation of study treatment are described in Section 6.2.3 and Section 10.

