# 6.2.4. Guidelines for Management of Immune-Related Adverse Events and Adverse Events of Clinical Interest

Therapy with immuno-oncology agents such as JNJ-63723283 may lead to specific irAEs that differ in nature, severity and duration as compared to AEs caused by agents with a different mode of action. Early recognition and management of these irAEs may mitigate more severe/subsequent toxicity. However, differential diagnoses including non-inflammatory etiologies as well as the impact of the underlying malignant disease and/or concomitant medication should be evaluated according to standard medical practice.

Management algorithms have been developed to assist investigators in assessing and managing specific irAEs following administration of nivolumab (SmPC; PI) and pembrolizumab (SmPC; PI). These guidelines are presented below and should be followed for JNJ-63723283. In addition to the management algorithms provided in following sections, it is recommended that

irAEs are managed according to the general treatment guidelines outlined for ipilimumab (PI). These guidelines recommend the following:

- 1. Subjects should be evaluated to identify any alternative etiology.
- 2. In the absence of a clear alternative etiology, all events of an inflammatory nature should be considered immune related.
- 3. Symptomatic and topical therapy should be considered for low-grade events.
- 4. Systemic corticosteroids should be considered for a persistent low-grade event or for a severe event.
- 5. More potent immunosuppressives should be considered for events not responding to systemic corticosteroids (eg, anti-TNF agents or mycophenolate).

If delaying the dose is necessary to ameliorate toxicity, follow the guidance in Section 6.2.2.

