## 6.2.4.1. Gastrointestinal Adverse Events

Diarrhea and colitis have been observed in subjects receiving anti-PD-1 therapies. Early recognition and treatment of diarrhea and colitis are critical to their management (see Table 9). Subjects should be advised to seek immediate medical evaluation if they develop new-onset diarrhea, blood in stool, or severe abdominal pain or if they have worsening of baseline diarrhea. In subjects with pre-existing diverticulosis or diverticulitis receiving concomitant medication with corticosteroids, nonsteroidal anti-inflammatory drugs (NSAIDs), and opioid analgesics together with anti-PD-1 therapies, diverticular perforation has been observed.

Guidelines for d	Guidelines for dose delay can be found in Section 6.2.2.		
Grade 1	Symptomatic treatment according to institutional standards		
Ulade I	Close monitoring; instruct subject to report worsening immediately and treat as Grade $\geq 2$		
	≤5 days: Symptomatic treatment according to institutional standards		
	>5 days or recurrence: 0.5–1.0 mg/kg/d methylprednisolone; consider prophylactic antibiotics;		
Grade 2	Persistence or worsening despite steroids >3 days: treat as Grade 3/4		
	Improvement to ≤Grade 1: taper steroids over at least 4 weeks, consider prophylactic antibiotics		
	for opportunistic infections, resume study therapy per protocol		
	Immediately: 1.0–2.0 mg/kg/d methylprednisolone IV; consider prophylactic antibiotics and		
	lower endoscopy		
Grade 3-4	Persistence >3 days or recurrence: add infliximab 5 mg/kg (if no contraindication such as		
	perforation or sepsis)		
	Improvement to $\leq$ Grade 2 within $\leq$ 3 days: taper steroids over at least 4 weeks		
	The oral corticosteroid equivalent of the recommended IV dose may be considered for		
General	ambulatory patients; the lower bioavailability of oral corticosteroids needs to be considered.		
	Clinical caution should be exercised, for subjects receiving concomitant medications of		
	corticosteroids, NSAID, or opioid analgesics. In addition, monitor for signs and symptoms of		
	potential perforation, especially in subjects with known diverticular disease. Narcotics should be		
	used with caution as pain medicines may mask the signs of colonic perforation.		

 Table 9:
 Management of Immune-Related Gastrointestinal Adverse Events

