## 6.2.4.7. Pulmonary Adverse Events

Pulmonary AEs including radiographic changes (eg, focal ground glass opacities and patchy infiltrates) indicative of drug-related pneumonitis have been observed in subjects receiving anti-PD-1 therapies. These pulmonary AEs were either asymptomatic or associated with symptoms such as dyspnea, cough, or fever. The initial occurrence of pulmonary AEs may be as early as after a single dose of anti-PD-1 therapies or delayed after prolonged therapy. Early recognition and treatment of pneumonitis is critical to its management (see Table 15). Subjects should be advised to seek medical evaluation promptly if they develop new-onset dyspnea, cough, or fever or if they have worsening of these baseline symptoms.

Guidelines for dose delay can be found in Section 6.2.2.		
	Monitor for symptoms every 2-3 days; consider pulmonary and infectious-disease consult;	
Grade 1	re-image every 3 weeks	
	Worsening: treat as ≥Grade 2	
	Monitor symptoms daily; re-image every 1-3 days; pulmonary and infectious-disease consultation;	
	consider bronchoscopy and lung biopsy; consider hospitalization	
Grade 2	Immediately: start 1.0 mg/kg/d methylprednisolone IV or oral equivalent; prophylactic antibiotics	
	Persistence for 2 weeks or worsening: treat as Grade 3-4	
	Improvement to ≤Grade 1 or baseline: taper steroids over at least 4 weeks	
	Hospitalize; pulmonary and infectious-disease consult; consider bronchoscopy and lung biopsy	
	Immediately: 2-4 mg/kg/d methylprednisolone or IV equivalent; add prophylactic antibiotics;	
Grade 3-4	Persistence for 2 days or worsening: add immunosuppression (eg, infliximab, cyclophosphamide,	
	IVIG, or mycophenolate mofetil)	
	Improvement to $\leq$ Grade 2: taper steroids over at least 6 weeks	
	Patients on IV steroids may be switched to an equivalent dose of oral corticosteroids	
General	(eg, prednisone) at start of tapering or earlier, once sustained clinical improvement is observed.	
	The lower bioavailability of oral corticosteroids need to be considered	

Table 15:Management of Pulmonary Adverse Events

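### Section 8.3 lists prolonged systemic corticosteroids among prohibited therapies and exempts only infusion reactions, through a wrong cross-reference, while Section 6.2.4 calls for courses above that limit for immune-related events

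*Protocol*

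**What the plan says.** Protocol Section 8.3 opens its list with "Use of the treatments listed below is prohibited during the study". The bullet on agents active against myeloma then turns to steroids above a dose and duration limit: "Systemic corticosteroids (>10 mg prednisone per day or equivalent for over 5 days) other than those given for IRRs". The exception, the cross-reference and the verb come together: "other than those given for IRRs, as described in Section 6.2.2 should be avoided". Section 8.3 closes by requiring that the sponsor be told, in advance or as soon as possible afterwards, whenever a prohibited therapy is given. Section 8 allows supportive medication apart from the Section 8.3 items, and Section 8.2 repeats that condition for symptom management.

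The section that is cross-referenced, 6.2.2, begins "Dose delay is the primary method for managing JNJ-63723283-related toxicities". It lists toxicities that require a delay, most of them immune-type. It mentions neither infusion reactions nor any corticosteroid regimen. Measures for infusion reactions are in Sections 6.1.2, 6.1.3 and 6.3.

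Section 6.2.4 introduces its management tables with "These guidelines are presented below and should be followed for JNJ-63723283". Tables 9 to 15 give methylprednisolone at 0.5 to 2 mg/kg/day for most event types. Grade 3-4 pulmonary events have a higher dose: "Immediately: 2-4 mg/kg/d methylprednisolone or IV equivalent". The usual instruction on improvement is to "taper steroids over at least 4 weeks"; for Grade 3-4 pulmonary events the minimum taper is 6 weeks. Section 6.2.3 requires treatment to stop if the steroid dose cannot be brought down to 10 mg of prednisone per day or less within 12 weeks.

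**The concern.** Section 6.2.4 asks for steroid courses that Section 8.3, read literally, places on the prohibited list. The only exception printed in Section 8.3 is for infusion reactions, and its cross-reference leads to text that does not deal with them.

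This bears on safety and on data handling. A site that reads Section 8.3 strictly might hold back treatment that Section 6.2.4 describes, or might give it and report it as prohibited therapy. Another site might treat the same course as routine supportive care and report nothing. The SAP plans a listing of major protocol deviations (Section 1.5, LSIDEV01), but neither document says how such a course would be classified.

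**Working it through.** No sample size, power or alpha figure is in dispute, so there is no figure of the plan to reproduce. The check is whether the Section 6.2.4 courses really cross the Section 8.3 limit, and whether any text exempts them.

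**Inputs**
- Limit (Section 8.3): more than 10 mg/day prednisone-equivalent for more than 5 days.
- Lowest tabulated systemic dose (for example Table 13, Grade 2-3 renal): 0.5 mg/kg/day methylprednisolone.
- Highest (Table 15, Grade 3-4 pulmonary): 4 mg/kg/day.
- Conversion (Attachment 2): 4 mg methylprednisolone = 5 mg prednisone, a factor of 1.25.
- Body weight: 80 kg, the weight used in Section 3.3 to equate 240 mg with 3 mg/kg; 60 to 100 kg is an assumed range.
- Taper: at least 4 weeks (28 days). The shape is not given, so a straight line to zero is assumed.

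**Dose.** Prednisone-equivalent D = weight × dose × 1.25.

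**Time above the limit during the taper.** Days = 28 × (1 − 10/D).

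| Weight | Methylprednisolone at 0.5 mg/kg | D | Multiple of 10 mg | Days above 10 mg |
|---|---|---|---|---|
| 60 kg | 30 mg | 37.5 mg | 3.75 | 28 × (1 − 10/37.5) = 20.5 |
| 80 kg | 40 mg | 50 mg | 5 | 28 × (1 − 10/50) = 22.4 |
| 100 kg | 50 mg | 62.5 mg | 6.25 | 28 × (1 − 10/62.5) = 23.5 |

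At 80 kg the highest dose is 320 mg methylprednisolone, or 320 × 1.25 = 400 mg prednisone-equivalent, 40 times the limit.

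The day counts leave out time at full dose before the taper starts, so they are low in that respect. They depend on the linear shape. A course could stay inside Section 8.3 only if all its time above 10 mg, full-dose days included, came to 5 days or fewer.

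**Exemption.** Sections 6.2.2 to 6.2.4 and 8 to 8.3 contain no statement that takes immune-related courses out of Section 8.3. Section 6.2.3 points the other way in substance. Its 12-week allowance for getting down to 10 mg assumes that subjects remain on study while above the dose that Section 8.3 names.

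**The case against.** The best defence is that the conflict is one of wording and that the intent is clear. The steroid sentence speaks of avoidance, not prohibition. The same list contains other softer items, such as the remarks on intravenous contrast and anti-inflammatory drugs. Section 6.2.3 plainly expects these courses. Some table entries only ask the investigator to consider steroids (Table 12 Grade 1-2, Table 14 Grade 2). Since Section 6.2.2 lists mostly immune-type toxicities, the infusion-reaction abbreviation in Section 8.3 may be a slip for immune-related events. Amendment 2 also stops the combination, so few new courses are likely.

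Much of this stands. To call it a breach is firm under the list heading but too strong for the sentence itself. The objection does not remove the defect, however. Heading and sentence disagree with each other, the notification rule attaches to the list, and Sections 8 and 8.2 treat the list as binding. If immune-related events were meant, the cross-reference still leads to a section with no steroid instructions.

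A reader might go further and infer that responses on the combination could be steroid responses, which would bias the response rate and progression-free survival in favour of Arm B. The protocol gives some ground for this: exclusion criterion 2 makes "emergency use of a short course of corticosteroids (equivalent of dexamethasone 40 mg/day for a maximum of 4 days" the only exception to its washout of antimyeloma treatment. The documents do not support the inference:
- It does not follow from the wording conflict, because the same courses could be given after the text is reconciled.
- No frequency of immune-related steroid use, or of response to it, is given.
- Both arms already receive methylprednisolone with daratumumab. In Cycle 1 this is 2 × 100 + 2 × 60 mg before infusions plus 40 mg after each of three or four infusions, or 440 to 480 mg.
- Safety Run-in subjects also receive JNJ-63723283, so the question is not confined to Arm B.
- Protocol Section 11.12 leaves no hypothesis testing, Section 17.9.1.1 drops Part 3, and SAP Section 1.6 reports efficacy only as a subject listing.

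**Conclusion.** The inconsistency is in the current text and should be corrected. Immune-related steroid courses under Section 6.2.4 exceed the Section 8.3 limit even at the lowest tabulated dose: 3.75 to 6.25 times the daily amount over 60 to 100 kg, and roughly 20 to 24 days above 10 mg against 5. The dose multiple rests only on Attachment 2 and body weight. The day count also rests on the assumed linear taper. The cross-reference to Section 6.2.2 is wrong for infusion reactions on any reading.

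The finding concerns conflicting instructions and their reporting consequence. It does not establish bias in any efficacy result. Recounting responses or censoring progression-free survival at the start of a steroid course is not warranted, because the plan has no comparative efficacy analysis for that to test. Such rules would also fall almost entirely on JNJ-63723283 recipients.

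A smaller reporting gap remains. LEFRSP01 has no steroid field. General concomitant medications are summarised (TSICM01), while the medication listings cover only pre- and post-infusion drugs. Immune-mediated events are listed with dates (LSFAE07), so some cross-reading is possible, but the dates of steroid courses are not printed.

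**What to change.** Reconcile Sections 8.3, 6.2.2, 6.2.3 and 6.2.4 so that they state:
- which section the exception in Section 8.3 refers to;
- whether infusion reactions were intended there;
- whether the steroid item is prohibited or to be avoided;
- whether corticosteroid courses for immune-related events fall under the Section 8.3 sponsor-notification rule.

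This review takes no position on which clinical rule is right. The cost is a few sentences of protocol text.

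Optionally, add to LEFRSP01 a flag for any response in a JNJ-63723283 recipient (Safety Run-in or Arm B) first documented after a corticosteroid course for an immune-related event. The shell shows the date of best response, so the date of first response would have to be derived for the flag. Its sort note names only Arms A and B, so the Safety Run-in group should be added. Section 8 already has systemic corticosteroids and drugs used to treat adverse events recorded in the case report form, so this needs programming but no new data.
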